#### % predicted FVC

As for FEV1 above.

#### % predicted FEF25-75

As for FEV1 above.

Reasons for spirometry not being performed will be summarised, where available.

#### 17.4.2.4 O2 saturation

#### 17.4.2.4.1 Derivation

Oxygen saturation is measured at baseline (BLO2SATI), at each three monthly follow up visit (FLO2SATI) and any unscheduled visits that may occur (UVO2SATI). No manipulation of these variables is required.

#### 17.4.2.4.2 Analysis

The analysis of  $O_2$  saturation is identical to the analysis of %predicted FEV1 described in 17.4.2.3.2 above.

#### 17.4.2.5 Growth and nutritional status - height, weight and body mass index

Growth is only relevant for children that are still growing, and the age at which children stop growing is different for every child. This study's participants include infants, children, adolescents and adults. For this outcome, it is important to use appropriate measurements for each age-group to capture how growth and nutritional status may have been affected by treatment received. There is no one global measurement that can be used for all ages. For this reason, separate analyses are proposed for children and adults: BMI z-score, height z-score and weight z-score in children; and BMI for adults. The centre type paediatric/adult at randomisation will be used to define child/adult for the purpose of analysis.

#### 17.4.2.5.1 Derivation

#### Children

Height (cm) (BLHGHTR, FUHGHTR), weight (kg) (BLWGHTR, FUWGHTR) and age (date of visit minus date of birth) are measured at baseline and at each three monthly follow up visit, respectively. Body mass index (BMI) will be calculated using the standard equation:

$$BMI = \frac{\text{weight}}{(\text{height}/100)^2}$$
[Eq2]

where height is measured in cm. The WHO 0-60 months of age reference curves [8] will be used to convert BMI to BMI z-scores in children aged less than 5. A SAS macro from WHO [9] will be used for all conversions. The WHO 5-19 years of age reference curves [10] will be used to obtain BMI z-scores for children aged 5-19. A SAS macro from WHO [11] will be used for all conversions. Height and weight reference curves [10] will be used to obtain height and weight z-scores.

#### Adults

Height (cm) (BLHGHTR, FUHGHTR), weight (kg) (BLWGHTR, FUWGHTR) are measured at baseline and at each three monthly follow up visit, respectively. Body mass index (BMI) will be calculated as in Eq2 above.

#### 17.4.2.5.2 Analysis

#### Children

The analyses of height, weight and BMI z-scores are identical to the analysis of %predicted FEV1 described in 17.4.2.3.2 above.

#### Adults

The analysis of BMI is identical to the analysis of %predicted FEV1 described in 17.4.2.3.2 above.

#### 17.4.2.6 Number of pulmonary exacerbations

At the design stage of this study, classification of a pulmonary exacerbations (Y/N) was defined using guidelines by Rosenfeld [4] and data collection was designed to enable this classification to be made.

#### 17.4.2.6.1 Derivation

Pulmonary exacerbations are defined using guidelines by Rosenfeld [4]. They propose a score system for deciding whether the patient is experiencing a pulmonary exacerbation. The score is calculated as follows:

 $PE_{score} = 1.8 \times I_1 + 1.5 \times I_2 + 1.5 \times I_3 + 1.6 \times I_4 + 1.2 \times I_5 + 1.1 \times I_6 - 3.1$  [Eq3]

where  $I_1 = 1$  if decreased exercise tolerance 'present'; 0 otherwise

 $I_2 = 1$  if increased cough 'present'; 0 otherwise

 $I_3 = 1$  if increased sputum/cough congestion 'present'; 0 otherwise

 $I_4 = 1$  if school or work absenteeism 'present'; 0 otherwise

 $I_5$  = 1 if increased adventitial sounds on lung examination 'present'; 0 otherwise

 $I_6 = 1$  if decreased appetite 'present'; 0 otherwise.

If the  $PE_{score} > 2.6$  then the patient is experiencing a pulmonary exacerbation.

If any indicators  $I_1 - I_6$  are coded as missing for whatever reason, they will be assigned the value 0 on the assumption that if the symptom is absent.

Pulmonary exacerbations criteria are captured at baseline and on all follow up visit CRFs along with any unscheduled visit CRFs that may be completed. They relate to the 2 weeks prior to the follow-up visit.

The total number of exacerbations recorded per child during the first 15 months of follow-up is the number of visits for which  $PE_{score} > 2.6$ . Note, we expect that all exacerbations will be measured, as they would usually result in the need for an unscheduled visit.

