#### 8.4.3 Removal of patients from therapy or assessment

Patients are free to withdraw from trial follow-up at any point, patients who do so will have data collected up to the point of withdrawal included in analyses unless they explicitly state that this is not their wish. Reasons for withdrawal will be captured where provided. See Section 14.2 below.

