#### 17.4.2.6.2 Analysis

The number of exacerbations during the first 15 months follow-up will be summarised with median and interquartile range for each treatment arm. A Mann-Whitney U-test will test whether the distribution of number of exacerbations is the same in each treatment arm. The number and percentage of patients experiencing at least one exacerbation in each treatment arm will also be reported. Treatment groups will be compared using the chi-squared test. The Fisher's exact test may be used if the chi-squared test is not appropriate (counts of <5 within categories).

Page 32 of 47

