#### 17.4.2.12.2 Analysis

For each microorganism, the number and percentage with at least one positive result will be presented split by treatment arm, and a relative risk and 95% confidence interval calculated. Chi-squared tests (or if necessary Fisher's exact test) will be used to test for differences between treatment groups.

Secondly, for each microorganism: the number and percentage with at least one positive result during the treatment phase; and by 15 months will be presented split by treatment-arm. Of those that were followed up to  $T_{24}$ , and for each microorganism, the number and percentage with at least one positive result by  $T_{24}$  will be presented split by treatment-arm.

Chi-squared tests will be used to test for differences between treatment groups.

Other organisms detected will be listed as a frequency table split by treatment arm. Frequencies presented will be the number of children with at least one positive culture of the organism during the study.

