#### 19.2.3.2 Analysis

The number and percentage of participants having had at least one exacerbation during the treatment phase, during the first year after treatment, and during the 2nd year after treatment will be presented. Denominators for percentages will be the number of patients followed up during the time-period within treatment arm, in preference to the number randomised.

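### The 15-month exacerbation outcomes and organism flags ignore follow-up time, so time not observed after withdrawal is scored as event-free

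*SAP*

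**What the plan says.** **Exacerbations (SAP 17.4.2.6).** The derivation reads "The total number of exacerbations recorded per child during the first 15 months of follow-up is the number of visits for which" the score is above 2.6. The analysis section says "A Mann-Whitney U-test will test whether the distribution of number of exacerbations is the same in each treatment arm", and adds "The number and percentage of patients experiencing at least one exacerbation in each treatment arm will also be reported", compared by chi-squared or Fisher's exact test. Neither section mentions length of follow-up.

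**Other microbiology (SAP 17.4.2.12).** MRSA, *B. cepacia* complex, Candida and Aspergillus each get a flag of 1 if a detection is dated before 15 months after randomisation, and 0 in every other case. In the analysis, "For each microorganism, the number and percentage with at least one positive result will be presented split by treatment arm", with a relative risk and a chi-squared or Fisher test. The 15-month comparison has no follow-up condition. The T24 summary does have one: it begins "Of those that were followed up to" T24.

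**Withdrawals.** Section 8.4.3 says that patients who leave follow-up "will have data collected up to the point of withdrawal included in analyses unless they explicitly state that this is not their wish". Section 17.1 limits each analysis to randomised patients whose outcome was observed or measured, rules out imputation, and names loss to follow-up as a possible reason for exclusion. Section 18 refers the handling of withdrawals back to the individual derivations.

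**Additional analyses, exacerbations only.** Section 19.2.2 plans time to first exacerbation, censored at last follow-up, with Kaplan-Meier curves and a log-rank test. Section 19.2.3.2 gives percentages by period and states: "Denominators for percentages will be the number of patients followed up during the time-period within treatment arm, in preference to the number randomised".

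**The concern.** A patient who leaves at month 4 with no positive visit contributes a count of zero for 15 months, exactly like a patient who was seen throughout and stayed well. The same patient, with no cultures after month 4, contributes a negative 15-month flag for all four organisms. Section 18 relies on the derivations to deal with withdrawal, and these two derivations do not.

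The trial is open label and compares an intravenous with an oral regimen, so unequal loss to follow-up between arms is possible. If it occurs, the arm that loses more patients is observed for less time, records fewer events and appears better with no true difference. The Mann-Whitney and chi-squared tests would then exceed their nominal 5% error rate.

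**Working it through.** The SAP states no figure on this point, so there is none to reproduce. It also gives no withdrawal rate, event rate or sample size (the last is left to the protocol). Everything numerical below is an assumption, except the 15-month horizon, the 1:1 allocation and the two-sided 5% level.

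**Step 1: how the SAP treats follow-up in comparable outcomes.**
- Primary outcome (17.4.1.1): a patient with no positive sample and no sample in the T15 window is excluded. Sections 19.1.1 and 19.1.2 add all-success and all-failure analyses.
- Hospital admission (17.4.2.7.1): depends on the T3 and T15 visits, or the next visit as a proxy.
- Carer burden (17.4.2.15.1): depends on the T15 visit, or an estimate from the next visit.
- Microbiology at T24: limited to patients followed to T24.
- 15-month exacerbation count, any exacerbation, and 15-month organism flags: no condition.

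**Step 2: size when withdrawal is spread evenly over 15 months.** Assume the same Poisson mean L per 15 months in both arms, and non-informative withdrawal with probability w.
- Mean recorded count = L(1 − w/2).
- P(at least one event recorded) = (1 − w)(1 − e^−L) + w[1 − (1 − e^−L)/L].

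Count ratio at 15% v 5%: 0.925/0.975 = 0.95. At 25% v 5%: 0.875/0.975 = 0.90.

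Any event with L = 1:
- w = 5%: 0.95 × 0.632 + 0.05 × 0.368 = 0.619
- w = 15%: 0.85 × 0.632 + 0.15 × 0.368 = 0.592, relative risk 0.96
- w = 25%: 0.75 × 0.632 + 0.25 × 0.368 = 0.566, relative risk 0.915

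Over L = 0.2 to 2 the relative risk is 0.95 to 0.97 at 15% v 5%, and 0.90 to 0.93 at 25% v 5%. At 10% v 10% every ratio is 1.00.

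**Step 3: size when all withdrawals fall at month 5.** With L = 1, P(any event) is 1 − e^−1 = 0.632 with full follow-up and 1 − e^(−1/3) = 0.283 at month 5.
- 25% v 5%, any event: 0.75 × 0.632 + 0.25 × 0.283 = 54.5%, against 0.95 × 0.632 + 0.05 × 0.283 = 61.5%.
- 25% v 5%, count ratio: (0.75 + 0.25/3)/(0.95 + 0.05/3) = 0.86.
- 15% v 5%, count ratio: (0.85 + 0.15/3)/(0.95 + 0.05/3) = 0.93, somewhat worse than with even spread.
- For L = 0.5 to 2, the any-event relative risk at 25% v 5% is 0.87 to 0.91.

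**Step 4: false-positive rate.** Simulation with the Step 2 assumptions, 75 to 200 patients per arm, L = 0.5 to 2 and 1,500 replicates per scenario:

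| Withdrawal | Mann-Whitney type I error | Poisson rate test with follow-up offset |
|---|---|---|
| 10% v 10% | about 5% to 6% | about 5% to 6% |
| 15% v 5% | about 5% to 12% | about 4% to 5% |
| 25% v 5% | about 7% to 34% | about 4% to 5% |

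**Step 5: a tempting repair that fails.** Suppose early leavers are set to missing only when they had no event. In the Step 3 case at 25% v 5%, the share remaining is 1 − 0.25 × 0.717 = 0.821 against 1 − 0.05 × 0.717 = 0.964. The proportions become 0.545/0.821 = 66.4% and 0.615/0.964 = 63.8%, a relative risk of 1.04. The bias is now in the other direction.

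**The case against.** The best defence is section 17.1. It restricts each analysis to patients whose outcome was observed, forbids imputation, requires membership of each analysis set to be documented before the randomisation lists are requested, and allows exclusion for loss to follow-up. A patient lost at month 4 could be left out of a 15-month outcome on that basis. This is a fair reading, particularly for the count. But the section does not say when a 15-month count or flag has been observed, 8.4.3 points towards inclusion, and the organism derivation assigns zero to everyone without a recorded detection. The conflict itself needs settling. Moreover, if 17.1 removed only early leavers without an event, it would produce the reverse bias of Step 5.

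Second, the exacerbation outcome is partly covered. Section 19.2.2 censors properly and shows Kaplan-Meier curves by arm as well as a log-rank test, and 19.2.3 uses followed-up denominators. This stands for any exacerbation. However, these are additional analyses: the first concerns first events only and plans no effect estimate, and the second does not say whether being followed for part of a period is enough. Neither corrects the count, and microbiology has no counterpart.

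Third, section 14.2 provides a blind review of withdrawals and recognises that their timing may bias results. The change control table records no resulting change to 17.4.2.6 or 17.4.2.12. Section 14.2 also keeps patients who merely stop treatment in follow-up, so treatment burden need not lead to loss of data.

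The note in 17.4.2.6.1 that exacerbations should be captured through unscheduled visits helps only while a patient remains in the trial.

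**Conclusion.** The point holds for the listed secondary outcomes. As written, the 15-month exacerbation outcomes and the four organism flags treat unobserved time as event-free, and the SAP does not settle whether early leavers belong in the denominator.

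Three stronger inferences are not supported:
- A reader might infer that every early leaver is recorded as event-free. Events before withdrawal are kept; only the time afterwards is lost.
- A reader might infer that the arm with more withdrawals must look better. That requires withdrawal to differ by arm and not to be strongly related to outcome, and the SAP contains no withdrawal rates to show a difference.
- A reader might infer that the main result is affected. The primary outcome has its own exclusion rule and sensitivity analyses.

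The size depends wholly on assumption. With equal true rates and evenly spread withdrawal, the false ratio is about 0.95 to 0.97 at 15% v 5%. Across the two timing patterns it is about 0.86 to 0.93 at 25% v 5%. It is 1.00 when non-informative withdrawal is equal. With modest imbalance the distortion is small. The change is worth making because it is cheap and the SAP already handles follow-up in neighbouring outcomes.

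**What to change.** - **Count (17.4.2.6.2):** compare arms with a negative binomial model, with log of follow-up time to T15 or withdrawal as offset, and report a rate ratio with 95% CI. Keep the Mann-Whitney test as supportive.
- **Any exacerbation, and each organism by 15 months:** report Kaplan-Meier proportions at T15 by arm, censoring at last visit (exacerbations) or last culture (organisms), with the difference or ratio and its 95% CI. For exacerbations this builds on the curves already planned in 19.2.2.
- **Do not** set only event-free early leavers to missing.
- **State in 17.1, 17.4.2.6 and 17.4.2.12** how patients who leave before T15 enter each analysis, so that these sections agree with 8.4.3.
- **Report** follow-up time by arm.

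The cost is SAP wording and modest programming with visit and sample dates already on the CRFs. The downside is a distributional assumption for the count. Both methods also assume non-informative withdrawal, so they remove the effect of unequal follow-up time but not bias from withdrawal related to outcome.

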#### 9.2 Secondary outcomes

- 1. Time to reoccurrence of original *P.aeruginosa* infection
- 2. Re-infection with a different genotype of *P.aeruginosa*
- 3. Lung function  $FEV_1$ , FVC,  $FEF_{25-75}$ ,
- 4. O2 saturation
- 5. Growth and nutritional status height, weight and body mass index
- 6. Number of pulmonary exacerbations
- 7. Admission to hospital
- Number of days spent as an inpatient in hospital during treatment phase and between three and fifteen months after randomisation.
- 9. Quality of life (CFQ)
- 10. Utility (EQ-5D)
- 11. Adverse events
- 12. Other sputum/cough Microbiology (Methicillin resistant *Staphylococcus aureus* (MRSA), *Burkholderia cepacia* complex, Aspergillus, Candida Infection)
- 13. Cost per patient (from NHS perspective)
- 14. Incremental cost effectiveness ratio (cost per successfully treated patient, cost per QALY)
- 15. Carer burden (absenteeism from education or work)
- 16. Participant burden (absenteeism from education or work)

<sup>1 Defined according to Rosenfeld criterion [4]

<sup>2 Protocol wording for this outcome is: "Number of days spent as inpatient in hospital over the threemonth period after allocated treatment has finished, treatment and between three months and 15 months after eradication treatment has finished-finished (other than 14 days spent on initial IV treatment)". Changed above to aid clarity.

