## 12 Confidence Intervals, p-values and Multiplicity

All applicable statistical tests will be two-sided and will be performed using a 5% significance level; confidence intervals presented will be 95%. No adjustment will be made for multiplicity for the secondary outcomes.

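### The exacerbation count in SAP 17.4.2.6.1 counts positive visits rather than episodes, so one episode seen at visits close together is counted more than once

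*SAP*

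**What the plan says.** SAP section 9.2 lists "Number of pulmonary exacerbations" as secondary outcome 6. Section 17.4.2.6.1 computes a symptom score at each visit and calls the patient exacerbating when it exceeds 2.6. It then states: "The total number of exacerbations recorded per child during the first 15 months of follow-up" "is the number of visits for which" the score is above that threshold.

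The symptom items are collected at follow-up visits "along with any unscheduled visit CRFs that may be completed". On the period covered, the section says: "They relate to the 2 weeks prior to the follow-up visit". It expects complete capture of exacerbations, "as they would usually result in the need for an unscheduled visit".

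Section 17.4.2.6.2 summarises the count by median and interquartile range and tests it: "A Mann-Whitney U-test will test whether the distribution of number of exacerbations is the same in each treatment arm". Section 12 sets the level: "All applicable statistical tests will be two-sided and will be performed using a 5% significance level". Section 17.4.2.6.2 also plans a chi-squared comparison of patients with any exacerbation. Section 19.2.2 adds time to first exacerbation, and section 19.2.3 adds a yes/no outcome by period.

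**The concern.** The outcome is named for an event, but the unit counted is a visit. The two agree only if each episode produces exactly one positive visit. The SAP's own account of capture makes that doubtful: an exacerbation is expected to bring the patient in outside the schedule, and a review soon afterwards, or a scheduled visit that happens to fall close by, can be positive again on much the same symptoms. Nothing in section 17.4.2.6 or section 19 sets a minimum gap, asks for recovery between positive visits, or merges neighbouring ones. The remark about unscheduled visits concerns missed episodes, not repeated ones.

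The count would then mix how often patients exacerbate with how often they are re-seen. Its Mann-Whitney test could respond to a difference in visiting when episodes are equally frequent, or a real difference in episodes could be masked.

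**Working it through.** The SAP gives no rate, power or expected count for this outcome, so there is no planned figure to reproduce. The check is a reading of the rule, followed by an illustration on assumed inputs.

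**1. The rule applied to one hypothetical patient.** T6 falls at 24 weeks, that is 24 × 7 = day 168 (SAP 8.9). Suppose one episode gives a positive unscheduled visit on day 155, a positive review on day 162 and a positive T6 visit on day 168. The gaps are 7 and 6 days, both inside the 14-day look-back. The rule returns 3 exacerbations for 1 episode.

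**2. Effect on the mean count.** Let E be the true number of episodes, Poisson with mean λ. Let each episode give one positive visit plus at most one repeat, with probability q. The count is V = E + Binomial(E, q), with mean λ(1 + q). For λ = 1.0, q = 0.2 gives 1.2 and q = 0.6 gives 1.6.

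**3. Effect on the planned summary.** The SAP reports median and interquartile range, not the mean. For λ = 1.0:

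- q = 0: P(V = 0) = 0.368, P(V ≤ 1) = 0.736, P(V ≤ 2) = 0.920.
- q = 0.6: P(V = 0) = 0.368. P(V = 1) = 0.368 × 0.4 = 0.147. P(V = 2) = 0.368 × 0.6 + 0.184 × 0.16 = 0.250. The cumulative values are 0.368, 0.515 and 0.765.

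In both cases the median is 1 and the quartiles are 0 and 2. The published summary could look identical in two arms while the test compares different distributions.

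**4. Effect on the test.** The simulation has no true difference in episodes, 125 patients per arm and a two-sided Mann-Whitney test at 5%. The sample size, the episode means and every repeat probability are assumptions.

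| Repeat probability, arm v arm | False rejection, episode mean 0.5 to 1.0 |
|---|---|
| 0.2 v 0.3 | about 5–7% |
| 0.2 v 0.4 | about 7–13% |
| 0.2 v 0.6 | about 12–35% |

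With 0.2 in both arms and a mean of 1.0, rejection stays near 5%. A more extreme 0.2 v 0.8 at a mean of 1.0 gives about 61–63%. The effect grows with the episode rate: at a mean of 2 and 100 to 140 per arm, 0.2 v 0.4 gives about 24–33%. Counting true episodes kept rejection at about 4–6% in every setting tried.

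**5. Reach.** Whether a patient had any positive visit, and when the first one occurred, does not change if later visits repeat it. The chi-squared comparison and section 19.2.2 are therefore unaffected. The by-period outcome in section 19.2.3 changes only if one episode spans a period boundary and enters both periods.

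**The case against.** Several points against this are fair.

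- Both arms follow the same schedule, with visits 12 weeks apart, so two visits within 14 days normally need at least one unscheduled visit. How often a review produces a scored form depends on protocol and form instructions that are not at hand.
- A repeat positive is not automatic. The item weights must sum to more than 2.6 + 3.1 = 5.7, and the three largest give only 1.8 + 1.6 + 1.5 = 4.9, so at least four of the six items must be present again.
- Only one of two planned tests, on one of 16 secondary outcomes, is exposed.
- The 14-day look-back is a recall window, not the duration of an exacerbation, so a rule built on it is only a partial remedy.

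These points limit the size and reach of the problem. They do not supply the missing rule. The unscheduled visits that can cluster are the ones the SAP relies on for capture, and section 8.9 reports many visits outside their windows. For hospital stay, sections 17.4.2.7 and 17.4.2.8 set detailed rules and sensitivity analyses for visit data that straddle periods; nothing comparable is given here.

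A reader might infer that the comparison between arms is biased because the trial is open label. The SAP does not support that. Open-label treatment makes different review habits possible, but nothing in the document shows them, least of all after the treatment phase, which leaves 12 of the 15 months counted. A reader might also infer that a reported mean will be inflated, or that every exacerbation analysis is compromised. The SAP reports no mean for this outcome, and the analyses named in step 5 of the working are essentially immune.

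**Conclusion.** The point holds for the count and its Mann-Whitney test. As written, the rule can count one episode two or more times, so the derived variable is not the number of exacerbations it is named for. This follows from the text and needs no assumption.

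The size does rest on assumptions. With equal repeat visiting the mean count is multiplied by 1 + q and the test keeps its size. With unequal repeat visiting, false rejection runs from barely above 5% to about 35% across the table in the working, depending on the imbalance and the episode rate. None of those inputs comes from the SAP, so the range shows sensitivity and does not predict this trial's error. It is worth correcting because the outcome is a named secondary outcome and no other planned analysis estimates the number of episodes.

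**What to change.** In section 17.4.2.6.1, count episodes instead of visits. A positive visit starts a new exacerbation only if it falls more than 14 days after the previous positive visit; otherwise its look-back overlaps the earlier one and it belongs to the same episode. Settle this analysis rule, with clinical agreement on the gap, before the randomisation lists are requested. Keep the raw visit count as a sensitivity analysis.

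The cost is a sentence or two in the SAP and a date-gap step in the program, using visit dates already held. The downsides should be stated with the rule:

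- Separate episodes 14 days apart or less would be merged.
- Chains can merge episodes much further apart: positive visits on days 1, 14, 27 and 40 have gaps of 13 days each and would become one episode.
- A long episode seen more than 14 days apart, such as on days 155 and 172 (a gap of 17 days), would still count twice.
- An episode that resolves more than 2 weeks before the next visit would still be missed, so some dependence on visit frequency remains.
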